7.1 Expected Toxicities

7.1.1 Adverse Events

7.1.1.1 Adverse Event Expected with Pembrolizumab (MK-3475, Keytruda)⁴

Clinical Trial Experience (selected portions of US Prescribing Information using the melanoma population as the disease with the greatest clinical experience).

Because clinical trials are conducted under widely varying conditions, adverse reaction rates observed in the clinical trials of a drug cannot be directly compared to rates in the clinical trials of another drug and may not reflect the rates observed in practice.

The data described in the WARNINGS and PRECAUTIONS section and below reflect exposure to KEYTRUDA in an uncontrolled, open-label, multiple cohort trial (Trial 1). In Trial 1, the safety data are available from 411 patients with unresectable or metastatic melanoma and 550 patients with metastatic NSCLC who received KEYTRUDA at either 2 mg/kg every 3 weeks (n=61) or 10 mg/kg every 2 or 3 weeks (n=489).

Among the 411 patients with metastatic melanoma enrolled in Trial 1, the median duration of exposure to KEYTRUDA was 6.2 months (range 1 day to 24.6 months) with a median of 10 doses (range 1 to 51). The study population characteristics were: median age of 61 years (range 18 to 94), 39% age 65 years or older, 60% male, 97% white, 73% with M1c disease, 8% with brain metastases, 35% with elevated LDH, 54% with prior exposure to ipilimumab, and 47% with two or more prior systemic therapies for advanced or metastatic disease.

KEYTRUDA was discontinued for adverse reactions in 9% of the 411 patients. Adverse reactions, reported in at least two patients, that led to discontinuation of KEYTRUDA were: pneumonitis, renal failure, and pain. Serious adverse reactions occurred in 36% of patients receiving KEYTRUDA. The most frequent serious adverse drug reactions reported in 2% or more of patients in Trial 1 were renal failure, dyspnea, pneumonia, and cellulitis.

Table 9 presents adverse reactions identified from analyses of 89 patients with unresectable or metastatic melanoma who received KEYTRUDA 2 mg/kg every three weeks in one cohort of Trial 1. Patients had documented disease progression following treatment with ipilimumab and, if BRAF V600 mutation positive, a BRAF inhibitor. This cohort of Trial 1 excluded patients with severe immune-related toxicity related to ipilimumab, defined as any Grade 4 toxicity requiring treatment with corticosteroids or Grade 3 toxicity requiring corticosteroid treatment (greater than 10 mg/day prednisone or equivalent dose) for greater than 12 weeks; a medical condition that required systemic corticosteroids or other immunosuppressive medication; a history of pneumonitis or interstitial lung disease; or any active infection requiring therapy, including HIV or hepatitis B or C. Of the 89 patients in this cohort, the median age was 59 years (range 18 to 88), 33% were age 65 years or older, 53% were male, 98% were white, 44% had an elevated LDH, 84% had Stage M1c disease, 8% had brain metastases, and 70% receive two or more prior therapies for advanced or metastatic disease. The median duration of exposure to KEYTRUDA was 6.2 months (range 1 day to 15.3 months) with a median of nine doses (range 1 to 23). Fifty-one percent of patients were exposed to KEYTRUDA for greater than 6 months and 21% for greater than 1 year.

KEYTRUDA was discontinued for adverse reactions in 6% of the 89 patients. The most common adverse reactions (reported in at least 20% of patients) were fatigue, cough, nausea, pruritus, rash, decreased appetite, constipation, arthralgia, and diarrhea.

	KEYTRUDA 2 mg/kg every 3 wee N=89			
Adverse Reaction	All Grades (%)	Grade 3* (%)		
General Disorders and Administration Site Conditions		(70)		
Fatigue	47	7		
Peripheral Edema	17	1		
Chills	14	0		
Pyrexia	11	0		
Gastrointestinal Disorders		0		
Nausea	30	0		
Constipation	21	0		
Diarrhea	20	0		
Vomiting	16	0		
Abdominal pain	12	0		
Respiratory, Thoracic and Mediastinal Disorders				
Cough	30	1		
Dyspnea	18	2		
Skin and Subcutaneous Tissue Disorders		1		
Pruritus	30	0		
Rash	29	0		
Vitiligo	11	0		
Metabolism and Nutrition Disorders		1		
Decreased appetite	26	0		
Musculoskeletal and Connective Tissue Disorders				
Arthralgia	20	0		
Pain in extremity	18	1		
Myalgia	14	1		
Back pain	12	1		
Nervous System Disorders		1		
Headache	16	0		
Dizziness	11	0		
Blood and Lymphatic System Disorders		12 12		
Anemia	14	5		
Psychiatric Disorders				
Insomnia	14	0		
Infections and Infestations				
Upper respiratory tract infection	11	1		

Table 9: Adverse Reactions in ≥10% of Patients with Unresectable or Metastatic Melanoma

* There were no Grade 5 adverse reactions reported. Of the ≥10% adverse reactions, none was reported as Grade 4.

Other clinically important adverse reactions observed in up to 10% of patients treated with KEYTRUDA were:

Infections and infestations: sepsis

	KEYTRUDA 2 mg/kg every 3 weeks N=89				
Laboratory Test	All Grades %	Grades 3-4 %			
Chemistry					
Hyperglycemia	40	2*			
Hyponatremia	35	9			
Hypoalbuminemia	34	0			
Hypertriglyceridemia	25	0			
Increased Aspartate Aminotransferase	24	2*			
Hypocalcemia	24	1			
Hematology		200			
Anemia	55	8*			

Table 10: Laboratory Abnormalities Worsened from Baseline in ≥20% of Patients with Unresectable or Metastatic Melanoma

* Grade 4 abnormalities in this table limited to hyperglycemia, increased aspartate aminotransferase, and anemia (one patient each)

Immune-Related Adverse Events

An irAE is defined as a clinically significant AE of any organ that is associated with study drug exposure, is of unknown etiology, and is consistent with an immunerelated mechanism. The most commonly reported immune-related adverse events across the dose-schedules in patients with melanoma were rash, pruritus, vitiligo, hypothyroidism, arthralgia, diarrhea, and pneumonitis. All occurred in less than 5% of patients. The organ most frequently affected by irAEs with pembrolizumab is the skin. Less frequently affected tissues include thyroid gland, colon, lung, kidney, and liver.

These events can occur after the first dose to several months after the last dose of treatment. Mild irAEs are usually treated symptomatically and do not require dosing delays or discontinuation. Higher grade and persistent lower grade irAEs typically necessitate withholding or discontinuing treatment and administration of systemic steroids or other immunosuppressive agents (such as tumor necrosis factor blockers), when systemic steroids are not effective. Early recognition of irAEs and initiation of treatment are critical to reduce the risk of complications, since the majority of irAEs are reversible with the use of steroids and other immune suppressants.

Immune-mediated adverse reactions

- Pneumonitis
- Colitis
- Hepatitis
- Nephritis and renal dysfunction
- Endocrinopathies:
 - o Hypophysitis
 - o Type 1 diabetes mellitus including diabetic ketoacidosis
 - Thyroid disorders: hyperthyroidism, hypothyroidism

- Pancreatitis
- Guillain-Barre Syndrome
- Myositis
- Arthritis
- Uveitis (<1%)
- Severe skin reactions: exfoliative dermatitis (<1%)
- Infusion reactions (severe: <0.1%)
- Hemolytic anemia
- Vasculitis
- Partial seizures related to inflammatory foci in brain parenchyma
- Serum sickness
- Myasthenia gravis

Select potential immune-mediated adverse reactions

Table below presents select treatment-related, potential immune-mediated adverse reactions that occurred in patients receiving KEYTRUDA. In addition, across clinical studies with KEYTRUDA in approximately 5000 patients, induction of type 1 diabetes mellitus has been reported in 0.1% of patients.

Table 11: Select Treatment-related, Potential Immune-mediated Adverse Reactions

Adverse Reaction		EYTRUDA every three n=162		KEYTRUDA 2 mg/kg every 3 weeks or 10 mg/kg every 2 or 3 weel n=411				
	All Grades (%)	Grade 3 (%)	Grade 4* (%)	All Grades (%)	Grade 3 (%)	Grade 4*		
Colitis [†]	1.2	1.2	0	1.0	0.5	0		
Hepatitis ¹	1.2	0	0.6	0.5	0	0.2		
Hyperthyroidism	0.6	0	0	1.0	0.2	0		
Hypophysitis	1.2	0	0.6	0.5	0	0.2		
Hypothyroidism	9.3	0	0	8.3	0.2	0		
Nephritis [§]	0	0	0	0.7	0.2	0.2		
Pneumonitis	1.2	0.6	0	2.7	0.2	0		

* There were no Grade 5 treatment-related potential immune-mediated adverse reactions reported with KEYTRUDA.

Includes colitis microscopic

[‡] Includes autoimmune hepatitis

Includes autoimmune nephritis and renal failure with evidence of interstitital nephritis

7.1.1.2 Adverse Events Expected with Radium-223³

Bone Marrow Suppression

In the randomized phase 3 trial, 2% of patients on the radium-223 arm experienced bone marrow failure or ongoing pancytopenia compared to no patients treated with placebo. There were two deaths due to bone marrow failure and for 7 of 13 patients treated with radium-223, bone marrow failure was ongoing at the time of death. Among the 13 patients who experienced bone marrow failure, 54% required blood transfusions. Four percent (4%) of patients on the radium-223 arm and 2% on the placebo arm permanently discontinued therapy due to bone marrow suppression.

In the randomized trial, deaths related to vascular hemorrhage in association with myelosuppression were observed in 1% of radium-223-treated patients compared to 0.3% of patients treated with placebo. The incidence of infection-related deaths (2%), serious infections (10%), and febrile neutropenia (<1%) were similar for patients treated with radium-223 and placebo. Myelosuppression; notably thrombocytopenia, neutropenia, pancytopenia, and leukopenia; has been reported in patients treated with radium-223. In the randomized trial, complete blood counts (CBCs) were obtained every 4 weeks prior to each dose and the nadir CBCs and times of recovery were not well characterized. In a separate single-dose phase 1 study of radium-223, neutrophil and platelet count nadirs occurred 2 to 3 weeks after radium-223 administration at doses that were up to 1 to 5 times the recommended dose, and most patients recovered approximately 6 to 8 weeks after administration.

Clinical Trials Experience

In the randomized clinical trial in patients with metastatic castration-resistant prostate cancer with bone metastases, 600 patients received intravenous injections of 50 kBq/kg (1.35 microcurie/kg) of radium-223 and best standard of care and 301 patients received placebo and best standard of care once every 4 weeks for up to 6 injections.² Prior to randomization, 58% and 57% of patients had received docetaxel in the radium-223 and placebo arms, respectively. The median duration of treatment was 20 weeks (6 cycles) for radium-223 and 18 weeks (5 cycles) for placebo.

The most common adverse reactions ($\geq 10\%$) in patients receiving radium-223 were nausea, diarrhea, vomiting, and peripheral edema. Grade 3 and 4 adverse events were reported among 57% of radium-223-treated patients and 63% of placebo-treated patients. The most common hematologic laboratory abnormalities in radium-223-treated patients ($\geq 10\%$) were anemia, lymphocytopenia, leukopenia, thrombocytopenia, and neutropenia.

Treatment discontinuations due to adverse events occurred in 17% of patients who received radium-223 and 21% of patients who received placebo. The most common hematologic laboratory abnormalities leading to discontinuation for radium-223 were anemia (2%) and thrombocytopenia (2%).

The Table below shows adverse reactions occurring in $\ge 2\%$ of patients and for which the incidence for radium-223 exceeds the incidence for placebo.

 Table 12: Adverse Reactions in the Randomized Trial of Radium and best standard of care vs. placebo and best standard of care

System/Organ Class	Xofigo	(n=600)	Placebo	o (n=301) Grades 3-4 %	
Preferred Term	Grades 1-4 %	Grades 3-4 %	Grades 1-4 %		
Blood and lymphatic sys	tem disorders	6		20 10	
Pancytopenia	2	1	0	0	
Gastrointestinal disorde	rs				
Nausea	36	2	35	2	
Diarrhea	25	2	15	2	
Vomiting	19	2	14	2	
General disorders and a	dministration site con	ditions	5. 		
Peripheral edema	13	2 10		1	
Renal and urinary disor	ders	d.	85	3.	
Renal failure and 3 mpairment		1	1	1	

Laboratory Abnormalities

The Table below shows the hematologic laboratory abnormalities occurring in $\geq 10\%$ of patients and for which the incidence for radium-223 exceeds the incidence for placebo.

Table 13: Hematologic Laboratory Abnormalities

Hematologic	Xofigo	(n=600)	Placebo (n=301)			
Laboratory Abnormalities	Grades 1-4 %	Grades 3-4 %	Grades 1-4 %	Grades 3-4 %		
Anemia 93		6	88	6 7		
Lymphocytopenia	mphocytopenia 72		53			
Leukopenia	35	3	10	<1		
Thrombocytopenia	31	3	22	<1		
Neutropenia	18	2	5	<1		

Laboratory values were obtained at baseline and prior to each 4-week cycle.

As an adverse reaction, grade 3-4 thrombocytopenia was reported in 6% of patients on radium-223 and in 2% of patients on placebo. Among patients who received radium-223, the laboratory abnormality grade 3-4 thrombocytopenia occurred in 1% of docetaxel naïve patients and in 4% of patients who had received prior docetaxel. Grade 3-4 neutropenia occurred in 1% of docetaxel naïve patients and in 3% of patients who have received prior docetaxel.

Fluid Status

Dehydration occurred in 3% of patients on radium-223 and 1% of patients on placebo. Radium-223 increases adverse reactions such as diarrhea, nausea, and vomiting which may result in dehydration.

Injection Site Reactions

Erythema, pain, and edema at the injection site were reported in 1% of patients on radium-223.

Secondary Malignant Neoplasms

Radium-223 contributes to a patient's overall long-term cumulative radiation exposure. Long-term cumulative radiation exposure may be associated with an increased risk of cancer and hereditary defects. Due to its mechanism of action and neoplastic changes, including osteosarcomas, in rats following administration of radium-223 dichloride, radium-223 may increase the risk of osteosarcoma or other secondary malignant neoplasms. However, the overall incidence of new malignancies in the randomized trial was lower on the radium-223 arm compared to placebo (<1% vs. 2%; respectively), but the expected latency period for the development of secondary malignancies exceeds the duration of follow up for patients on the trial.

7.2 Adverse Event Characteristics

• **CTCAE term (AE description) and grade:** The descriptions and grading scales found in the revised NCI Common Terminology Criteria for Adverse Events (CTCAE) version 4.0 will be utilized for AE reporting. All appropriate treatment areas should have access to a copy of the CTCAE version 4.0. A copy of the CTCAE version 4.0 can be downloaded from the CTEP web site http://ctep.cancer.gov/protocolDevelopment/electronic_applications/ctc.htm.

• For expedited reporting purposes only:

- AEs for the agent(s) that are listed above should be reported only if the adverse event varies in nature, intensity or frequency from the expected toxicity information.
- **Attribution** of the AE:
 - Definite The AE *is clearly related* to the study treatment.
 - Probable The AE *is likely related* to the study treatment.
 - Possible The AE *may be related* to the study treatment.
 - Unlikely The AE *is doubtfully related* to the study treatment.
 - Unrelated The AE *is clearly NOT related* to the study treatment.

7.3 Expedited Adverse Event Reporting

A serious adverse event is any adverse event occurring at any dose or during any use of the study drugs that:

- Results in death;
- Is life threatening;
- Results in persistent or significant disability/incapacity;
- Results in or prolongs an existing inpatient hospitalization;
- Is a congenital anomaly/birth defect;
- Is a new cancer (that is not a condition of the study);
- Is associated with an overdose;
- Is another important medical event in the opinion of the treating physician or PI

• All bone fractures need to be reported as either AE(s) or SAEs if the criteria of SAE were met, regardless of the investigator's causality assessment for a minimum of 1 year after the last dose of radium-223. Taking into consideration applicable guidelines, bone health agents (BHA) such as bisphosphonates or denosumab are recommended.

From the time of consent up to study drug initiation, only serious adverse events deemed related to study procedures are required to be reported to the Overall PI. Investigators **must** report to the Overall PI any serious adverse event (SAE) that occurs after the initial dose of study treatment, during treatment, or within 90 days of the last dose of treatment on the local institutional SAE form.

Any serious adverse event, or follow up to a serious adverse event, deemed related to study procedures from the time of consent up to study drug initiation, must be reported within 24 hours to the Sponsor (DFCI) and within 2 working days to Merck Global Safety. Any serious adverse event, or follow up to a serious adverse event, including death due to any cause other than progression of the cancer under study, that occurs to any subject from the time of study drug initiation through 90 days following cessation of treatment, or the initiation of new anti-cancer therapy, whichever is earlier, whether or not related to Merck product, must be reported within 24 hours to the Sponsor (DFCI) and within 2 working days to Merck Global Safety.

Non-serious Events of Clinical Interest will be forwarded to Merck Global Safety and will be handled in the same manner as SAEs.

Additionally, any serious adverse event, considered by an investigator who is a qualified physician to be related to Merck product that is brought to the attention of the investigator at any time outside of the time period specified in the previous paragraph also must be reported immediately to the Sponsor and to Merck.

SAE reports and any other relevant safety information are to be forwarded to the Merck Global Safety [contact]

A copy of all 15 Day Reports and Annual Progress Reports is submitted as required by FDA, European Union (EU), Pharmaceutical and Medical Devices agency (PMDA) or other local regulators. Investigators will cross reference this submission according to local regulations to the Merck Investigational Compound Number (IND, CSA, etc.) at the time of submission. Additionally, investigators will submit a copy of these reports to Merck & Co., Inc. (Attn: Worldwide Product Safety;

All subjects with serious adverse events must be followed up for outcome.

For multi-institution studies where a DF/HCC investigator is serving as the Overall Principal Investigator, each participating institution **must** abide by the reporting requirements set by the DF/HCC. This applies to any medical event equivalent to an unexpected grade 2 or 3 with a possible, probable or definite attribution, all grade 4

toxicities (except those that are expected AND listed as not reportable in this protocol), and grade 5 (death) regardless of study phase or attribution.

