5.5 Duration of Follow Up

Participants will have a follow up visit within 30 days of removal from protocol therapy (End of Treatment visit). Adverse event monitoring will continue through End of Treatment visit. Subjects who discontinue for reasons other than progressive disease will have post-treatment follow-up for disease status until disease progression, initiating a non-study cancer treatment, withdrawing consent or becoming lost to follow-up. Follow up scans are not required for patients who do not progress, but will be captured if possible. After documented disease progression each subject will be followed by telephone, chart review, or clinic visit for overall survival until death, withdrawal of consent, or the end of the study, whichever occurs first. Regardless of reason for discontinuation, patients will be followed every 6 months until death or 2 years after treatment discontinuation.

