7.7 Routine Adverse Event Reporting

All Adverse Events **must** be reported in routine study data submissions to the Overall PI on the toxicity case report forms. **AEs reported through expedited processes (e.g., reported to the IRB, FDA, etc.) must** also be reported in routine study data submissions.

7.7.1 Definition of an Overdose for This Protocol and Reporting of Overdose to the Sponsor and to Merck

For purposes of this trial, an overdose of pembrolizumab will be defined as any dose of 1,000 mg or greater (\geq 5 times the indicated dose). No specific information is available on the treatment of overdose of pembrolizumab. Appropriate supportive treatment should be provided if clinically indicated. In the event of overdose, the subject should be observed closely for signs of toxicity. Appropriate supportive treatment should be provided if clinically indicated.

If an adverse event(s) is associated with ("results from") the overdose of a Merck product, the adverse event(s) is reported as a serious adverse event, even if no other seriousness criteria are met.

If a dose of Merck's product meeting the protocol definition of overdose is taken without any associated clinical symptoms or abnormal laboratory results, the overdose is reported as a non-serious Event of Clinical Interest (ECI), using the terminology "accidental or intentional overdose without adverse effect."

All reports of overdose with and without an adverse event must be reported within 24 hours to the Sponsor and within 2 working days hours to Merck Global Safety. (Attn: Worldwide Product Safety;

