13.8 Analysis of Secondary Endpoints

Safety and Tolerability: All adverse events recorded during the trial will be summarized for the safety population. The incidence of events that is new or worsening from the time of first dose of treatment will be summarized according to system organ class term, severity (based on CTCAE version 4.0 grade), type of adverse event, and relation to study treatment. For the combination therapy, special interests include toxicities related to induction of immune phenomenon such as pneumonitis, colitis, and severe rash. The frequency of AEs will be summarized separately according to treatment arms, with 90% exact binomial confidence intervals (CI). The proportion of patients in each arm with grade 4 or higher AEs will also be reported with an exact binomial 90% CI.

Deaths reportable as SAEs and non-fatal serious adverse events will be listed by patient and tabulated by primary system organ class, and type of adverse event.

PFS and OS: The distributions of time to PSA progression, PFS and OS will each be summarized using the product-limit method of Kaplan-Meier according to treatment arms. Median times for each endpoint will be presented with two-sided 95% confidence intervals estimated using log(-log(survival)) methodology. Kaplan-Meier estimates of the endpoints at 6 or 12 months after treatment initiation may also be presented with two-sided 95% confidence intervals.

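### The open-ended late SAE clause in 7.3 names only the Merck product, so, fractures and an undated DF/HCC rule aside, late related SAEs can enter the Arm A tables by a route that Arm B lacks

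*Combined protocol and SAP*

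**What the plan says.** Section 7.3 sets the all-cause SAE window twice. Reports to the Overall PI run to "within 90 days of the last dose of treatment on the local institutional SAE form". Reports to the Sponsor and to Merck's safety group run "through 90 days following cessation of treatment, or the initiation of new anti-cancer therapy, whichever is earlier, whether or not related to Merck product". Both apply to both arms.

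Outside the window, 7.3 adds a duty with no time limit for an SAE that a physician investigator considers "related to Merck product that is brought to the attention of the investigator at any time outside of the time period specified". That report goes to the Sponsor as well as to Merck.

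Two further rules in 7.3 are not tied to Merck's product. Bone fractures, whatever their cause, are reportable for at least 1 year after the last radium-223 dose. DF/HCC requirements, printed without a time window, cover unexpected grade 2 or 3 events with at least possible attribution, grade 4 toxicities with an exception, and all deaths.

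On the route into the results, 7.7 says that "AEs reported through expedited processes (e.g., reported to the IRB, FDA, etc.) must" also appear in the routine study data. Section 13.8 summarizes every AE recorded during the trial, gives AE frequencies separately by arm, and adds: "Deaths reportable as SAEs and non-fatal serious adverse events will be listed by patient and tabulated". It states no cut-off after the last dose.

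**The concern.** A safety comparison between arms needs the same events looked for over a comparable period. Here the only open-ended clause for related SAEs is written around the supplier of one drug. The title page lists pembrolizumab as Merck's and radium-223 as commercial supply, and 5.1 gives pembrolizumab to Arm A alone. The clause therefore cannot apply to an Arm B patient.

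The protocol itself recognizes that radium-223 may act late: 7.1.1.2 says "radium-223 may increase the risk of osteosarcoma or other secondary malignant neoplasms", 7.3 makes a new cancer an SAE criterion, and the fracture rule extends surveillance to at least a year. The extension stops at fractures.

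The stake is how the safety tables are read. Treatment-related AEs of grade 3 or higher are a secondary endpoint (13.1), and 13.5 says there are no safety data for this combination. Readers are likely to set the two arms side by side even though no test is planned.

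**Working it through.** The plan states no figure to reproduce. The check compares the reporting rules by agent, arm and time, then follows the data into the tables.

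**1. What is reportable after the all-cause window closes**

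| Event | Rule | Arms | Time limit |
|---|---|---|---|
| SAE related to pembrolizumab | 7.3, late clause | A only | none |
| Bone fracture, any cause | 7.3, fracture rule | A and B | at least 1 year after last radium-223 dose |
| Certain grade 2 to 4 events; all deaths | 7.3, DF/HCC rule | A and B | not stated |
| Other SAE related to radium-223 | no explicit clause | neither | not applicable |

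The last row is the gap. It is defined by agent: an Arm A event attributed to radium-223 alone also falls outside the late clause. It becomes a difference between arms because a late Arm A event can be attributed at least partly to pembrolizumab and so be reported, while an Arm B event cannot.

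**2. When the window closes in each arm**

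The window runs from the end of treatment, and treatment length differs. With no delays and the maximum number of doses:

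- Arm B (5.1): six doses every 4 weeks. Last dose at week 1 + 5 × 4 = 21. Adding 90 / 7 = 12.9 weeks, the window closes near week 34.
- Arm A (5.4): up to 35 pembrolizumab doses every 3 weeks. Last dose at week 1 + 34 × 3 = 103. Adding 12.9 weeks, the window closes near week 116.

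These are upper limits; progression, toxicity or new therapy shortens them. They show that a radium-223 SAE one year after the last radium-223 dose can still fall inside the all-cause window for an Arm A patient on pembrolizumab, while the same event in Arm B falls outside it.

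**3. From report to table**

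Routine AE recording ends 30 days after treatment (section 7, introduction). Section 7.7 then adds expedited reports to the study data, and 13.8 summarizes whatever is recorded, by arm, with no cut-off. That a late report enters the by-arm tables is an inference from these two sections; nothing in 13.8 excludes it.

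**4. Scale**

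The 2:1 allocation of 45 patients gives 30 and 15. One SAE is 1/15 = 6.7 percentage points in Arm B and 1/30 = 3.3 in Arm A.

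The documents give no late-onset SAE rate. The nearest figures are whole-trial rates for radium-223 in the phase 3 trial (7.1.1.2): marrow failure or ongoing pancytopenia 2%, new malignancies below 1%. For 15 patients these give 15 × 0.02 = 0.3 and fewer than 15 × 0.01 = 0.15 events over all time. They indicate small numbers and are not estimates of the late excess.

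**The case against.** The strongest reply is that the plan already looks past the window without regard to Merck's product, and that nothing depends on the remainder. Much of this stands.

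- **Other rules.** The fracture rule covers both arms. Footnote Q of the study calendar collects survival, next therapies and symptomatic skeletal events in both arms, and under 5.5 "patients will be followed every 6 months until death or 2 years after treatment discontinuation". If the DF/HCC rule were read as open-ended, it would also catch deaths and most grade 4 toxicities, leaving mainly expected grade 2 or 3 radium-223 events. It prints no time limit, however, so it cannot be relied on to close the gap.
- **Passive reporting.** A reader might infer that Arm A has full late ascertainment. It does not. The clause waits for an event to reach the investigator; AE monitoring ends at the End of Treatment visit (5.5), and the six-monthly contacts do not ask about AEs in either arm.
- **Marrow failure.** A reader might cite the statement that in 7 of 13 radium-223 patients "bone marrow failure was ongoing at the time of death" as evidence of late onset. It shows persistence. An event starting inside the window is reportable in both arms, and 7.3 requires SAEs to be followed for outcome.
- **Consequence.** The by-arm AE summaries are descriptive with 90% intervals and no between-arm test. The safety review in 13.5 uses the first 15 Arm A patients after 12 weeks of combination therapy, and the primary endpoint comes from biopsies.

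What remains is narrow: no clause covers a late non-fracture SAE related to radium-223, and no stated window keeps the by-arm tables comparable.

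**Conclusion.** The point holds as a minor drafting gap that is cheap to close. Late related SAEs have an explicit, unlimited route into the data for pembrolizumab and none for radium-223 beyond fractures and whatever the DF/HCC rule reaches. The longer possible treatment in Arm A widens the difference in observation time.

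A reader might go further and infer that late radium-223 SAEs in Arm B go uncounted altogether, that only pembrolizumab-related events count for most of the 2-year follow-up, or that the combination will look measurably more toxic. The documents do not support these readings. The fracture rule contradicts the first two. The third needs an assumed late risk and needs every late Arm A event to be attributed to pembrolizumab, although a risk common to both arms could equally come from the shared drug and would then lack the clause in both.

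The effect is probably a very small number of events, and its size cannot be derived from the documents. The conclusion assumes that 7.7 and 13.8 mean what they say, so that late expedited reports are tabulated. The primary endpoint and the early safety review are untouched.

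**What to change.** In the paragraph of 7.3 on SAEs that come to light outside the window, change the condition for reports to the Sponsor to *related to pembrolizumab or radium-223*. The copy to Merck can stay as written.

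In 13.8, state that the by-arm SAE tables cover first dose to 90 days after the last dose of any study agent, in both arms. Show time at risk per arm beside the counts, because treatment duration differs. List later related SAEs separately for both arms.

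The cost is one phrase in 7.3 and a short addition to 13.8, plus a few extra late reports. The six-monthly contacts already scheduled give sites an occasion to learn of such events; no visit is added.
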